6.4 STUDY INTERVENTION COMPLIANCE

Study adherence will be assessed primarily through blood and respiratory ketosis values, both directly via beta-OHB phlebotomy at defined intervals (three times daily) and indirectly via POC glucose checks, continuous glucose monitors, and daily respiratory quotient (pCO₂/pO₂, expected to decrease from approximately 1.0 towards 0.7 as a function of predominantly glucose to predominantly fatty acid metabolism). Adherence will be assessed also through records of diet consumption made by Nutrition Department staff (AI) using instructions to consume 100% of provided meals and weighing meals before/after consumption, logging data using ProNutra software. All willing study participants will be counseled on ketogenic diet in preparation for the outpatient portion of the study unless they have communicated that they will decline the outpatient study. They will receive a schedule of possible meals to select from for the two weeks of outpatient study and to establish a means of contact with study nutritionists for adherence estimation. During these two weeks, study nutritionists will call them twice weekly at unscheduled times for 24-hour food recall review, and data from these calls will be used to determine outpatient adherence.

Abbreviated Title: Tolerability and efficacy of ketogenic diet in Parkinson's Disease

Version Date: 04/19/2021

6.5 CONCOMITANT THERAPY

For this protocol, a prescription medication is defined as a medication that can be prescribed only by a properly authorized/licensed clinician. Medications to be reported in the Case Report Form (CRF) are concomitant prescription medications, over-the-counter medications and supplements.

No adjustments will be made to patient's home medication regimen including all Parkinson's Disease medications. Any omissions whether in error or patient choice will be recorded in CRIS.

7. STUDY INTERVENTION DISCONTINUATION AND PARTICIPANT DISCONTINUATION/WITHDRAWAL

7.1 DISCONTINUATION OF STUDY INTERVENTION

Discontinuation from dietary intervention does not mean discontinuation from the study, and remaining study procedures should be completed as indicated by the study protocol. If a clinically significant finding is identified (including, but not limited to changes from baseline) after enrollment, the investigator or qualified designee will determine if any change in participant management is needed. Any new clinically relevant finding will be reported as an adverse event (AE).

Holding criteria: Study intervention(Liquigen® (KetoCal)) and ketogenic diet) will be withheld if clinically significant cardiac arrhythmia is detected on baseline ECG (please refer to Clinical Evaluations Section 8.2 for details).

The data to be collected at the time of study intervention discontinuation will include the following:

- diet menu and record
- patient interview with worksheets and symptoms
- height, weight, vital signs including orthostatic (supine x 10min, immediately and 3min after standing); physical examination with focused neurologic examination

Stopping criteria:

- 1.) Patient request
- 2.) If any investigator judges that continuing the procedure would be detrimental to the patient's health and well-being or that clinically meaningful data is not being obtained for other reasons.

An investigator may discontinue or withdraw a participant from the study for the following reasons:

- Completion of study intervention
- Disease progression which requires discontinuation of the study intervention
- If any clinical adverse event (AE), laboratory abnormality, or other medical condition or situation occurs such that continued participation in the study would not be in the best interest of the participant
- Investigator discretion
- Positive pregnancy test
- Participant unable to receive study intervention for more than 1 day

Abbreviated Title: Tolerability and efficacy of ketogenic diet in Parkinson's Disease

Version Date: 04/19/2021

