- Outcomes:** The primary outcome is feasibility, as determined by a composite outcome of recruitment and retention, acceptability and adherence, including full recruitment to study target of 32 participants; completion rate >80% in both inpatient 1-week and outpatient 2-week segments; adherence in the outpatient segment of estimated low carbohydrate diet <10% mean total

Abbreviated Title: Feasibility and efficacy of ketogenic diet in Parkinson's Disease

Version Date: 04/19/2021

daily energy defined as net carbs); and acceptability defined via exit survey (week 3) 4-point Likert efficacy and likelihood scales on how effective ketogenic diet appears on symptoms and how likely ketogenic diet, with or without MCT oil, participants estimate they will continue the diet on at least an intermittent basis in the future.

The secondary outcome is Timed up & go (TUG) mean difference between groups at the end of admission (day 7).

Exploratory outcomes include both group comparisons (mean difference) at day 7 and repeated measures days 1-7 between MCT-KD and SAD groups (in most but not all outcomes; refer to section 1.3 Schedule of Activities for details) and at week 3, when both groups combine to a single ketogenic diet group, and within-group pre vs. post intervention comparisons at 1 & 3 weeks for both groups separately (SAD at 0 & 2 weeks of ketogenic diet vs. MCT-KD group at 1 & 3 weeks, respectively) and all participants, in the following: Stroop word-color interference latency (executive function), n-back recall task (attention and working memory), finger tap speed and rhythm (MN and PQ keyboard tasks), accelerometry amplitude for tremor analysis; 9-hole pegboard test (9-HPT) (daily), heart rate variability HF power, total power (resting, daily), cardiovagal testing via deep breathing and Valsalva Maneuver (pre vs. post), mean subjective on vs. off time (pre vs. post), non-motor severity score (NMSS) pre vs. post, keto-induction symptoms, UPDRS (pre vs. post), EEG spectral power by frequency and connectivity analysis (day 1 vs. day 7 vs. week 3), Geriatric Depression Scale (GDS, pre vs. post)

Study Population:

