Abbreviated Title: Tolerability and efficacy of ketogenic diet in Parkinson's Disease**Version Date:** 04/19/2021

POG glc checks		X	X	X	X	X	X	X	
Beta-OHB level twice daily, except once on day 7****		X	X	X	X	X	X	X	X**** *
Procedures	Screening	Day 1	Day 2	Day 3	Day 4	Day 5	Day 6	Day 7 / Post	W 3 (post)
Plasma dopamine twice daily		X	X	X					
Continuous glucose monitoring (Precision Libre Pro)		X	X	X	X	X	X	X	
n-back working memory test daily (exploratory outcome)		X	X	X	X	X	X	X	X
Stroop word color interference test daily (exploratory outcome)		X	X	X	X	X	X	X	X
MN and PQ keyboard tasks		X	X	X	X	X	X	X	X
Safety monitor (telephone interview) survey 2-4 weeks post-study completion									X
Depression screening tool: Geriatric Depression Scale (GDS)	X							X	X
Gastrointestinal motility / symptoms diary (daily days 1-7)		X	X	X	X	X	X	X	

Abbreviated Title: Tolerability and efficacy of ketogenic diet in Parkinson’s Disease

Version Date: 04/19/2021

Gastrointestinal Symptom Rating Scale	X	X						X	X
Exit Survey acceptability of ketogenic diet									X
Tracking diet via unscheduled calls*****	X								X
*No Day 0 (7 days of baseline diet and history, then Day 1 is first day of admission) **women of childbearing potential ***repeat BMP and magnesium on days 6 and 7 if abnormal in prior days ****check beta-OHB in fasted state at week 3 visit ***** To occur during week between screening visit/enrollment and day 1 of admission and during 2 weeks after day 7. See Section 4.1 for details.									

Abbreviated Title: Tolerability and efficacy of ketogenic diet in Parkinson's Disease

Version Date: 04/19/2021

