3. OBJECTIVES AND ENDPOINTS

OBJECTIVES	OUTCOME MEASURES	JUSTIFICATION FOR ENDPOINTS
Primary		
Feasibility of MCT-KD x three weeks	Composite outcome (all of the following measures must be met):	MCT-KD has never been studied in PD population (expected to

Abbreviated Title: Tolerability and efficacy of ketogenic diet in Parkinson's Disease**Version Date:** 04/19/2021

	
1) Recruitment reaches target of 32 participants or as per pre-set interim analysis
 
2) Study retention rate >80% of all participants at 3 weeks
 
3) Adherence ($\leq 10\%$ mean daily energy from net carb over 2 weeks MCT-KD outpatient, assessed by 2x/week unscheduled phone calls by CC Nutrition staff)
 
4) Acceptability – Likert scale ≥ 2 (at least somewhat likely to use diet in future and at least somewhat effective in improving PD symptoms) at end of study (week 3)
	augment ketosis) and feasibility has not been established.
Secondary		
Timed Up & Go (TUG) time, mean difference between groups on study day 7	Mobility on the Timed Up and Go (TUG) test, daily (fastest of three trials per session) units: seconds Range: 8-18s	TUG time is generally regarded as an index of fall risk – estimated 20% risk reduction with 4s faster time (Nocera et al, 2013)
Tertiary/Exploratory		

Nutritional ketosis (NK) improves PD symptomatology at three weeks in the following: in cognition (improved attention, recall, and executive function), and motor function (reduced akinesia and tremor). A low fat (standard American) diet (SAD) does not.
 
NK reduces non-motor symptoms, subjective motor fluctuations and daily off time within the immediate keto-induction period, while SAD does not (mean difference at 1
	
Stroop word-color interference latency (unit: ms, range: 110-135 ms), 0,1,2,3 back recall task (unit i: % error of missing true n-back letter presented; range i: 0-back 0-10%, 1-back 4-20%, 2-back 15-30%, 3-back 20-32%; unit ii reaction time (RT) ms, range ii 0-back 500-740 ms; 1-back 600-980 ms; 2-back 700-1200 ms; 3-back 700-1200 ms); fingertap speed and rhythm (MN and PQ keyboard tasks; units MN and PQ keystroke speed, in keys/s; range MN
	
All of these tests have been shown to be impaired in PD cohorts and are at least semi-quantitative and amenable to serially repeated measures with good test-retest reliability
 
Scalp EEG is non-invasive, easy to perform in the setting of intervention, and as

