8.2 EFFICACY ASSESSMENTS

As one of the study aims is to determine feasibility of MCT supplemented ketogenic diet, the efficacy of primary objective of study feasibility as per recruitment, retention, acceptability, and adherence will be determined by a composite outcome, in which all criteria are met: completion rate of both inpatient 1 week and outpatient 2 week segments, with target of >80% for each; recruitment target of 32 participants reached; adherence to outpatient diet with mean daily carb $\leq 10\%$; intervention is acceptable to all participants by Likert scale $\geq 2/4$ of likelihood of using this therapy in the future and effectiveness in symptom reduction.

Efficacy of secondary objective of TUG reduction will be assessed by between-group mean difference at 7 days (MCT-KD vs. SAD). It is presumed that the standard (control) diet will not provide any issues of feasibility. Refer to Section 4.1 Study Design for direct and indirect determinations of ketosis.

Timed Up & Go (TUG)

Efficacy of TUG will also factor effect of time, via repeated measures ANOVA for TUG that will be tested three times per session and fastest time used, with same timing relation to dopaminergic medications.

Efficacy will be tested further in the between group difference between the two diets on outcomes of the following, again with same timing regarding dopaminergic medications:

Exploratory measures will be done as per test schedule in Section 4.1, generally once daily or less.

Stroop Word-Color Interference

this test has been shown to be impaired in PD as part of the executive network of actively choosing the stimulus while inhibiting the background. The latency will be determined from a computer test.

N-Back Task (% correct)

This test (Kirchner, 1958) involves a series of visual stimuli such as letters, and then participants are asked if each stimulus matches a stimulus n trials before. Performance is shown to be impaired in PD to a greater degree than in normal aging

Simple Reaction Time (SRT)

SRT (same cue on computer screen, press button; machine is used already for Chronic Fatigue Syndrome protocol studies and will be made available for the study). PD is consistently shown to have increased latency that is attributed to the akinesia as cardinal motor symptom. The increase in latency is reduced by

Abbreviated Title: Tolerability and efficacy of ketogenic diet in Parkinson's Disease

Version Date: 04/19/2021

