1 STATISTICAL CONSIDERATIONS

9.1 STATISTICAL HYPOTHESIS

Primary hypothesis:

Nutritional ketosis supplemented by MCT oil is feasible within a Parkinson Disease cohort as defined by an acceptable retention rate and outpatient adherence.

Primary outcome: Feasibility of nutritional ketosis(ketogenic diet with 80% lipid including MCT oil, 10-15% protein, 5-10% carbohydrate), in Parkinson Disease cohort defined as a composite outcome meeting all of the following criteria: recruitment target of 32 or as per interim power analysis defined in Section 9.4.6; retention rate > 80% at study end; adherence to ketogenic diet in the outpatient portion defined as mean carbohydrate energy intake <10%, and intervention is acceptable to all participants by Likert scale \geq 2/4 of likelihood of using this therapy in the future and effectiveness in symptom reduction, from all study participants at 3 weeks.

Secondary hypothesis:

Abbreviated Title: Tolerability and efficacy of ketogenic diet in Parkinson's Disease

Version Date: 04/19/2021

Nutritional induced ketosis (NK) increases mobility based on TUG score in a Parkinson Disease cohort at 7 days compared to usual diet (35% lipid, 10-15% protein, 50-55% carbohydrate). Secondary outcome: timed Up & Go test (TUG score) at study day 7 (fastest of three trials)

$H_0: \mu_1 = \mu_2$, where μ_1 and μ_2 are the population means for the NK diet group and usual diet group respectively vs. $H_1: \mu_1 \neq \mu_2$.

Exploratory hypotheses:

Hypothesis A: Nutritional ketosis improves PD symptomatology in cognition (improved attention, recall, and executive function, and motor function akinesia and tremor within six days, as assessed by: Stroop word-color interference latency (executive function), n-back recall task (attention and working memory), simple reaction time (akinesia); fingertap speed and rhythm MN and PQ keyboard tasks (fine motor), and autonomic function (heart rate variability at rest and with deep breathing / Valsalva Maneuver tests)

Hypothesis B: The mechanism of symptomatic reduction of NK in PD is both augmented mitochondrial metabolism (direct, rapid) and augmented neurotransmitter and growth factor synthesis (indirect, delayed), especially GABA and dopamine, as assessed by resting state EEG spectral power, phase coherence, and M1 waveform normalization. Accordingly, effect sizes for exploratory outcomes will be greater at 3 weeks than 7 days.

Exploratory outcomes daily (days 1-7), week 3

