9.2 SAMPLE SIZE DETERMINATION

Power analysis was performed based second outcome, TUG score, rather than feasibility outcome due to clinical significance of the former for both mobility and fall risk that is felt to be an important justification for this intervention as a pilot study, whereas feasibility ascertainment does not justify the study but merely indicates lack of existing clinical use of this ketogenic diet protocol.

Abbreviated Title: Tolerability and efficacy of ketogenic diet in Parkinson's Disease

Version Date: 04/19/2021

Considering range of TUG tests reported in Parkinson's Disease off dopaminergic medication of 8-17s (Foreman 2011), mean of 10-15s with SD 2.15-3.7s (Foreman 2011, Brusse 2005, Dal Bello-Haas 2011), and association of 1s increase in TUG time with 5.4% increase in odds of reporting a fall (Nocera 2013), it is suggested that fall rate can be reduced by 20% with a 4s reduction in TUG time, which is therefore considered to be a clinically meaningful difference. Minimal detectable change is reported as 4.85s (Dal Bello-Haas 2011) and 3.5s (Huang 2011).

Based on these studies, the difference of 4.5s between the group means, which was considered as clinically important, and standard deviation (SD) of 4s (or effect size of 1.125) were used for power analysis. A two-sample t-test was applied to estimate sample size by assuming that the primary outcome, TUG, followed normal distributions, and the variances of the two groups were equal. Power analysis indicated that a total of 28 subjects, 14 per group, will be needed to achieve a power of 80% to detect the difference of 4.5s at significant level of 0.0492. The sample size calculation considered one planned interim analysis scheduled to be conducted when 8 subjects per group have completed. Using O'Brien-Fleming approach, the interim analysis will be conducted with bound, $p=0.0054$ ($t\text{-value}=3.287$, $df=16$) and final analysis with bound $p=0.0492$ ($t\text{-value}=2.06$, $df=26$). By anticipating 10% dropout rate, we will need to recruit a total of 32 subjects (16 per group).

Randomization

Stratified randomization method will be used to control the covariates of age (≤ 65 vs. >65) and TUG baseline score (≥ 11.5 s, vs. <11.5 s Nocera 2013). With these two covariates, there are 4 possible block combinations (TUG ≤ 11.5 s & age ≤ 65 , TUG ≤ 11.5 s & age >65 , TUG >11.5 s and age ≤ 65 , TUG >11.5 s & age >65).

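### Acceptability is scored only at the week-3 exit survey, and the plan does not say how participants who leave earlier count in this required part of the primary composite

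*Combined protocol and SAP*

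**What the plan says.** Section 3 describes the primary endpoint as a "Composite outcome (all of the following measures must be met", with four parts: recruitment, retention, adherence and acceptability. The Synopsis gives the source of the last part: "acceptability defined via exit survey (week 3) 4-point Likert efficacy and likelihood scales". In the Schedule of Activities the row "Exit Survey acceptability of ketogenic diet" is marked at week 3 only, and Section 4.1 describes the survey as an online form.

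The denominator is worded differently from place to place. Sections 3 and 4.1 give the Likert threshold (at least 2) with no denominator. Section 8.2 requires that the "intervention is acceptable to all participants by Likert scale" threshold, and Section 9.1 asks for this "from all study participants at 3 weeks". Retention is a separate part: "Study retention rate >80% of all participants at 3 weeks".

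For early stopping, Section 7.1 states "The data to be collected at the time of study intervention discontinuation will include the following", then lists the diet record, an interview with worksheets and symptoms, physical measures and an examination. Section 7.2 adds a telephone safety contact and the reason for leaving. Neither section includes the exit survey. Section 9.4.1 says only that feasibility will be assessed descriptively, and Section 9.3 is a single line. Neither has a rule for a missing survey. Section 9.2 plans for losses: "By anticipating 10% dropout rate, we will need to recruit a total of 32 subjects".

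**The concern.** The people most likely to find the diet unacceptable are also the most likely to have left before the only occasion on which acceptability is measured. Several provisions lead from intolerance or unwillingness to departure:

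- Section 6.3 withdraws a participant after listed events, including vomiting, unless there is agreement to continue.
- Section 7.1 allows withdrawal of someone unable to receive the intervention for more than a day.
- Section 7.2 lists significant non-compliance as a reason for withdrawal.
- Sections 6.2.4 and 6.4 make the outpatient segment something that participants may decline.

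The protocol's own background (Section 2.3.2) reports that subjective tremor or rigidity accounted for half of the 4 ketogenic-arm dropouts in an earlier Parkinson's trial.

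Because the rule refers to all participants, one low score fails the component. Counted over completers, a dissatisfied participant who stays therefore fails the trial, while one who leaves does not. Counted over everyone enrolled, any leaver without a survey fails it. At stake is whether the primary outcome can be scored without a decision taken after the data are seen.

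**Working it through.** **Inputs.** Target 32 enrolled, 28 evaluable, 10% dropout, TUG difference 4.5 s, SD 4 s, two-sided level 0.0492 (Section 9.2). Retention above 80% (Section 3). Attrition in earlier ketogenic studies in Parkinson's disease of 28% and 18%, the latter with 9% attributed to diet (Table 1, Section 2.1).

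**Step 1: the plan's sample size.** The effect size is 4.5/4 = 1.125. The two-sample t-test (noncentral t) has power 78.4% with 13 per group and 81.5% with 14 per group, so 14 per group (28) is the smallest size reaching 80%. Then 28/0.9 = 31.1, which becomes 32 with equal groups. The plan's figures reproduce, and 32 is the base used below.

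**Step 2: how many can leave.** 25/32 = 78.1% fails and 26/32 = 81.25% passes. Up to 6 participants can therefore leave with retention still met.

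**Step 3: the two readings of acceptability, if every completer scores at least 2 and no leaver is surveyed.**

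| Leavers | Retention | Over completers | Over all enrolled |
|---|---|---|---|
| 0 | 32/32 = 100%, pass | 32/32, pass | 32/32, pass |
| 1 | 31/32 = 96.9%, pass | 31/31, pass | 31/32, fail |
| 3 (about 10%) | 29/32 = 90.6%, pass | 29/29, pass | 29/32 = 90.6%, fail |
| 6 | 26/32 = 81.25%, pass | 26/26, pass | 26/32 = 81.25%, fail |

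With 1 to 6 leavers, the reading alone decides the result.

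**Step 4: how often this arises at the planned dropout.** Assume that each of 32 participants leaves independently with probability 10%. The chance of at least one leaver is 1 − 0.9^32 = 96.6%. The chance that 26 or more stay is 96.4%. Retention would then nearly always pass, while the all-enrolled reading of acceptability would nearly always fail.

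**Step 5: the most that the completers reading could hide.** Assume, as an extreme, that every dissatisfied participant leaves and nobody else does. Let p be the true share who would score at least 2. These values of p are assumptions, not figures from the plan.

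| p | All 32 would score at least 2 (p^32) | Retention and completers-only acceptability both pass, P(at least 26 of 32) |
|---|---|---|
| 80% | 0.1% | 53.5% |
| 85% | 0.6% | 80.5% |
| 90% | 3.4% | 96.4% |
| 95% | 19.4% | 99.9% |

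**Step 6: the cited attrition figures.** 18% of 32 is 5.8, about 6, which is exactly the retention limit. The diet-attributed 9% is 2.9, about 3. 28% of 32 is about 9, leaving 23/32 = 72%, which fails retention however the surveys are handled. The gap therefore matters for attrition up to 18.75% (6/32), a range that includes the plan's own 10%.

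**The case against.** The list quoted from Section 7.1 concerns stopping the diet. That section opens by separating this from leaving the study and keeps the remaining procedures due. A reader might infer that everyone who rejects the diet is lost to the acceptability measure. The documents do not support that, because a participant who stops only the diet is still due the week-3 survey. Section 7.3 also provides for rescheduling and repeated contact after a missed visit. This part of the objection stands and confines the gap to people who actually leave or do not return.

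Leavers are also not invisible to the primary outcome, because they count against retention. Leaving and opinion after trying a diet are different things, and some withdrawals will have nothing to do with the diet. Scoring leavers as not acceptable counts them in two components. This stands in part. Retention tolerates six leavers and does not record what they thought, so it does not replace a rule for acceptability.

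A further inference would be that the plan drops dissatisfied leavers from the criterion and so biases acceptability upward. That is only one reading. The wording in Sections 8.2 and 9.1 does not restrict the criterion to completers and can equally mean everyone enrolled, in which case the error runs the other way.

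Finally, the earlier trials lasted longer (28 days and 8 weeks), and the half of dropouts mentioned in Section 2.3.2 is 2 people. They give context and do not predict attrition here.

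**Conclusion.** The point holds as a gap in the definition and collection of one required component. Acceptability has a single time of measurement, no collection at withdrawal, an unsettled denominator and no rule for a missing survey. With 1 to 6 of 32 leaving unsurveyed and all completers satisfied, the component passes on one reading and fails on the other. On the all-enrolled reading, the retention allowance has no effect, although the plan itself expects 10% dropout. Neither an upward bias nor a composite blind to all leavers is established.

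This rests on full recruitment of 32, on leavers not being replaced (Section 7.2 allows replacement only before the intervention is received), and on the 10% of Section 9.2 being a fair guide to losses over three weeks. The probabilities in Step 4 assume independent departures, and those in Step 5 are a worst case. There is no safety issue. The change is inexpensive and should be made before any outcome is reviewed.

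**What to change.** 1. In Sections 7.1 and 7.2, and in the Schedule of Activities, add the existing online exit survey to the assessments at early discontinuation or withdrawal for anyone who has begun the ketogenic diet.
2. In Sections 3, 8.2 and 9.1, use one denominator: all participants in either arm who began the ketogenic diet. Count a missing survey as not acceptable.
3. In the same sections, replace the all-participants requirement with a stated proportion. This must accompany item 2, since otherwise one unsurveyed leaver still fails the composite. To be attainable when retention only just passes and no leaver is surveyed, the proportion cannot exceed 26/32 = 81.25% if all 32 began the diet. The sponsor should choose and justify the value.
4. Report the completers-only figure as descriptive. List separately the standard-diet participants who leave before starting the ketogenic diet, since they cannot rate a diet they have not eaten.

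The cost is one short form at withdrawal, some rewording, and possibly a lower reported acceptability rate. Sample size and visits do not change.
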